#### **How Supplied**

Isordil® (isosorbide dinitrate) Oral Titradose® Tablets will be supplied as 5-15 mg tablets by the CCHMC pharmacy according to titration.

#### **Storage**

They are round, pink tablets with one deeply scored side. They are stable until the date noted. They should be stored at controlled room temperature at 25°C (77°F), with excursions permitted to 15-30°C (59-86°F). They should be kept in a light resistant bottles.

#### **Proposed Dose**

ISDN will be administered by the CCHMC investigational pharmacy for a 2 week period of titrating up the dose followed by 4 continuous weeks of dosing of maximum tolerable dose determined by weight. Patients will be dispensed medication in 5mg, 10mg and 20 mg doses, and each patient will be given a personalized schedule for titrating up in dosage. Dosage may require halving a pill. See Table 2.

Patient Weight	<40 kg	40-49 kg	≥50 kg
Visit 1, Starting Dose	0.25 mg/kg/d	5 mg	5 mg
Visit 2, Up To	0.50 mg/kg/d	10 mg	10 mg
Visit 3, Up To	0.75 mg/kg/d	15 mg	15 mg
Visit 4, Clinic Visit, Up To	1.0 mg/kg/d	20 mg	20 mg
Visit 5, Up to		x	30 mg

Patients >50 kg will have a target dose of 30 mg TID. Patients 40-49 kg will have a target dose of 20 mg TID. Patients <40 kg will have a target dose of 1 mg/kg/d. Patients >40 kg will be started on low dose ISDN therapy (5 mg TID) at first to ensure they tolerate the medication. A phone call will be made 3-5 days after initiation of therapy to inquire about symptoms, and adherence to medication. If the patient is tolerating the medication well, the dose will be increased to 10 mg TID. Once increased, another follow-up phone call 3-5 days later will be made for further inquiry about the medication tolerance and increased to 15 mg TID. After 15 mg is reached patient will be brought in to clinic to check blood pressure and draw BMP and increase the dose. In patients ≥50 kg, dose will be increased once more to 30 mg TID. Once the patient dose is stable, it will be continued for a 4 week trial. If patients are symptomatic or not tolerating the medication at follow-up phone call, attempts will be made to adjust background medications prior to lowering the ISDN dose and follow-up phone calls will be made at 3-5 days after any adjustment to therapy.

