### **Visit 4 (3 days [+/-1 day] after Visit 3)**

- Follow-up phone call to ensure patient tolerating medication and adjust medications

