### **Visit 6 (4 weeks after visit 3 [+/-2 days] before discontinuing ISDN)**

- Repeat vitals (heart rate, blood pressure, oxygen saturation, height and weight)
- Urine pregnancy test for all females
- Insertion of venous cannula for venous blood pressure during exercise testing and estimate of mean capillary filling pressure
- Maximal cardiopulmonary exercise testing/Ramp protocol (including spirometry)
- Liver ultrasound to assess for liver stiffness
- Recover medication vial
- Perform drug accountability
- Blood collection (Basic Metabolic Panel-3ml)

Table 1 presents schedule of procedures for this study.

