**Table 1: Patient Timeline**

	Visit 1	Visit 2	Visit 3	Visit 4	Visit 5	Visit 6
	Day 0	Day 3 (+/-1 day)	Day 6 (+/-1 day)	Day 9 (+/-1 day)	Day 12 (+/-1 day)	Day 34 (+/- 3 days)
Procedures:						
Informed consent	X					
Demographics and medical history	X					
Medication review	X					
Vital signs	X					X
Urine Pregnancy Test	X					X
Venous pressure a	X					X
Spirometry b	X					X
Maximal exercise ramp test	X					X
Liver Ultrasound	X					X
Quality of Life Survey	X					X
Medication dispensation	X					
Phone call to adjust medications		X	X	X	X	
Collect medication vial						X
Basic Metabolic Panel	X					X
Adverse event monitoring	X	X	X	X	X	X

a Venous pressure will be measured from before exercise test, every 1 minute during exercise, until 5 minutes after exercise.

b Spirometry will occur prior to maximal exercise testing

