#### *Pharmacologic Interventions*

At the conclusion of the first visit ISDN therapy will begin at a small dose (5 mg three times daily in those targeting 20-30 mg TID, less in patients < 40 kg) and be titrated up to goal three times daily over 2 weeks (see Table 2). The medication will be continued for 4 weeks once the target dose is reached. It is an organic nitrate commonly used to prevent angina and used frequently in heart failure as well. It acts upon vascular smooth muscles to cause vasodilation of the peripheral arteries and veins. It should be taken by mouth three times per day with water. It may be taken with or without food.

Patients not tolerating the medication will be instructed to call the clinic for adjustment of medications. Severe side effects to note include pre-syncope, syncope, and severe headache. The PI will assess the patient over the phone and ask them to come in if necessary. Conversation and any changes of

medications will be documented. Less severe symptoms such as mild lightheadedness or headache should attempt to be tolerated or treated with acetaminophen prior to calling the clinic.

Isosorbide dinitrate's clinically relevant interaction is with phosphodiesterase-5 inhibitors, a common medication in Fontan patients. There is a risk for excessive hypotension and therefore, will be a contraindication to enrollment in the trial. ISDN can also affect kidney function. For this reason, a basic metabolic panel will be taken at the start of the study and 1 week after initiation of ISDN.

Side effects will attempt to be reduced by a step-wise up-titration plan, use of acetaminophen for headache, and recommendation to return to previous dose if necessary which may enhance tolerability. Furthermore, patients will be followed up with by phone call 3-5 days after any change in medication.

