#### Venous puncture

A needle will be used to draw a basic metabolic profile at Visit 1 and Visit 6 to assess renal function. The minimal amount of blood (~2 mL) will be obtained one time at each visit.

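### The dosing section requires a Visit 4 clinic check of blood pressure and BMP, but the visit list and Table 1 make Visit 4 a phone call and schedule neither measurement between Visits 1 and 6

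*Combined protocol and SAP*

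**What the plan says.** The Proposed Dose section states: "After 15 mg is reached patient will be brought in to clinic to check blood pressure and draw BMP and increase the dose". In the dosing table there (Table 2), the row that takes patients of 40 kg or more from 15 to 20 mg, and lighter patients from 0.75 to 1.0 mg/kg/day, is headed "Visit 4, Clinic Visit, Up To".

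The operational sections differ. The visit list gives one item for Visit 4: "Follow-up phone call to ensure patient tolerating medication and adjust medications". Table 1 marks the row "Phone call to adjust medications" at Visits 2, 3, 4 and 5, and marks vital signs and the BMP only at Visits 1 and 6. The Venous puncture section agrees: "A needle will be used to draw a basic metabolic profile at Visit 1 and Visit 6 to assess renal function".

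Other sections fall between these positions:
- Pharmacologic Interventions gives a different time: "a basic metabolic panel will be taken at the start of the study and 1 week after initiation of ISDN". It mentions no blood pressure check.
- Potential Risks, Discomforts and Inconveniences counts three office visits. One is at two weeks, to look at blood pressure because of concern for the kidneys. The same section counts blood draws at only two visits.
- The Abstract and the Participation Cost section both assume two clinic visits.

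**The concern.** The protocol gives two incompatible instructions for the same contact, and one of them removes a safety measurement. A phone call cannot measure blood pressure or creatinine. Staff usually book visits and laboratory work from the schedule table. Anyone doing so here would take patients, some as young as nine, to full dose with no measurement since baseline. Asymptomatic or transient hypotension, or a change in renal function, could go unseen during titration.

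The Primary Objective begins with safety. Pharmacologic Interventions and the risk section name hypotension and kidney effects as the hazards to watch. The Proposed Dose section also directs that, in patients who do not tolerate the drug, background medications be adjusted before ISDN is lowered. Under Table 1 that decision would be made by phone without a current blood pressure or renal value. The DSMB first meets after two patients are enrolled, yet under Table 1 no patient has a scheduled on-treatment blood pressure or BMP until Visit 6.

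**Working it through.** The check is mainly a comparison of sections.

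| Section | Visit 4 or interim contact | Interim BP | Interim BMP |
|---|---|---|---|
| Proposed Dose, text | Clinic, after 15 mg | Yes | Yes |
| Proposed Dose, Table 2 | Visit 4 in clinic, all weight bands | Not stated | Not stated |
| Visit list, Visit 4 | Phone call | No | No |
| Table 1 | Visits 2-5 by phone | No (Visits 1, 6) | No (Visits 1, 6) |
| Venous puncture | Not addressed | Not addressed | No (Visits 1, 6) |
| Pharmacologic Interventions | Not stated | Not stated | Yes, at 1 week |
| Potential Risks | Third office visit, at 2 weeks | Yes | Draws at two visits only |
| Abstract | Two clinic visits in total | No | No |
| Participation Cost | Two paid visits in total | Not addressed | Not addressed |

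The conflict is not an artefact of table extraction. The prose of the visit list and of Venous puncture supports Table 1, and the prose of Proposed Dose supports Table 2.

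**Unmonitored interval under Table 1.** Visit 1 is Day 0 and Visit 6 is Day 34 ± 3, so the gap runs from 34 − 3 = 31 to 34 + 3 = 37 days. Proposed Dose describes 2 weeks of titration plus 4 weeks at stable dose, which is 14 + 28 = 42 days. The Table 1 figure is therefore the smaller one.

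**Dose increases in that interval (Table 2).**
- Under 40 kg: 0.25, 0.50, 0.75, 1.0 mg/kg/day, which is 3 increases.
- 40-49 kg: 5, 10, 15, 20 mg three times daily = 15, 30, 45, 60 mg/day, which is 3 increases.
- 50 kg or more: the same, then 30 mg three times daily = 90 mg/day, which is 4 increases.

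The third increase is the one made at Visit 4, and it is where Proposed Dose places the check.

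**Does Visit 4 match the other stated times?** It depends on which spacing rule is used.
- Table 1: Day 9 ± 1, so Day 8-10.
- Visit list, three steps of 3 ± 1 days: 3 × 2 = Day 6 to 3 × 4 = Day 12.
- The 3-5 day rule in Proposed Dose and Pharmacologic Interventions ("patients will be followed up with by phone call 3-5 days after any change in medication"): 3 × 3 = Day 9 to 3 × 5 = Day 15.

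The 1-week BMP (Day 7) fits only the early end of the visit-list range. The 2-week visit (Day 14) fits only the 3-5 day range. Table 1's own window contains neither.

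**Does the 15 mg trigger reach the lightest patients?** A patient under 40 kg at 1.0 mg/kg/day takes less than 40 mg/day, or less than 40/3 = 13.3 mg per dose if divided in three. The sentence's trigger is never met in this band, and only the Table 2 row label applies.

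**Payment.** The current total is 2 × $50 + $100 = $200. With three visits it is 3 × $50 + $100 = $250. Over 15 patients the added cost is 15 × $50 = $750.

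**The case against.** The conflict itself is plain on the page. The case against concerns its reach, its weight and the direction of the fix.

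- **Scope.** Table 2 says clinic visit but names neither measurement, and patients under 40 kg never reach the 15 mg trigger. This stands. Blood pressure and BMP at Visit 4 in that band is a sensible extension of the text, not a literal requirement.
- **Order.** The dosing sentence puts the check and the increase at one visit and does not require the BMP result to be seen first. This also stands, so the fix asks that the sample be drawn, not reported, before the increase.
- **Discretion.** The risk section's sentence on the two-week visit mentions investigator discretion. It is unclear whether that applies to holding the visit or to judging the blood pressure change. The dosing sentence carries no such qualifier, so the conflict remains.
- **Weight.** Table 1 contains no doses, so staff who raise the dose at Visit 4 must consult Table 2 or the patient's personalised schedule, and Table 2 shows the clinic label. Adverse events are monitored at every contact, phone calls follow each change, and safety laboratory values go to the DSMB. These limit the harm. They do not supply a measured blood pressure or creatinine when the schedule books none.
- **Direction.** Several sections consistently describe two visits, and no section states three draws. The sponsor must therefore confirm its intent. The dosing instruction, the 1-week BMP and the third office visit all point to an interim check, though, and dropping it would remove a safeguard that the protocol justifies on renal grounds.

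**Conclusion.** The concern holds. The protocol both requires and omits an in-clinic blood pressure and BMP check at Visit 4. Followed as Table 1 is written, patients go 31 to 37 days and through three or four dose increases with neither measurement scheduled. This is more than a clerical slip, because the version staff are likeliest to schedule from lacks a check the protocol relies on for named risks. It must be corrected.

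The consequence is confined to detecting asymptomatic or transient changes during up-titration. Visit 6 still captures both quantities on treatment, and the VO2 endpoint is untouched. The conclusion assumes that sites may schedule from Table 1 and the visit list. The DSMB charter was not among the documents available, and it may already ask for interim values.

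**What to change.** Make Visit 4 an in-clinic visit in the visit list and in Table 1, with vital signs and BMP marked. State that blood pressure is measured and the BMP drawn before the increase to 20 mg three times daily, or to 1.0 mg/kg/day in patients under 40 kg. Then align the rest with three clinic visits (1, 4 and 6) and three draws:
- Abstract: patients are seen three times.
- Pharmacologic Interventions: the second BMP is at Visit 4.
- Venous puncture: BMP at Visits 1, 4 and 6.
- Potential Risks: the two-week visit is Visit 4, and there are three blood draws.
- Participation Cost: payment covers three visits.

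Report the Visit 4 blood pressure and BMP values in the safety analysis and to the DSMB.

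The cost is a protocol amendment and, per patient, one clinic visit and one draw of about 2-3 mL. The dosing section already commits to both. Payment rises by $50 per patient, at most $750 in all; it would be less if the phone-call payment is reduced because one call becomes a visit, or if some participants are not from the paying centre. Patients who live far away make one more trip.

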### **Inclusion/Exclusion Criteria**

#### **Inclusion criteria:**

- Underlying Fontan physiology
- On a stable medication regimen for the past 3 months
- Nine years of age or older

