### **Baseline visit (Visit 1)**

- Informed Consent
- Baseline vitals (heart rate, blood pressure, oxygen saturation, height and weight)
- Demographic, medical, and medication review
- Urine pregnancy test for all females
- Blood collection (Basic Metabolic Panel-3ml)
- Insertion of peripheral venous cannula for venous blood pressure during exercise testing and estimate of mean capillary filling pressure
- Maximal cardiopulmonary exercise testing/Ramp protocol (including spirometry)
- Liver ultrasound to assess for liver stiffness
- Medication distribution

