#### **Potential Risks, Discomforts and Inconveniences:**

Potential risks, discomforts and inconveniences of this study include three office visits, two of which will require time and for the patient to undergo intravenous blood pressure measurement. Two of the visits will also require blood draw with similar risks. IV insertion could result in minimal bleeding, bruising and pain in a small portion of people. Furthermore, they will undergo exercise testing at two of these office visits, which is associated with arrhythmias in some patients and/or discomfort.

The risk associated with the medication, isosorbide dinitrate, are primarily due to hypotension which could lead to mild headaches or potentially severe systemic hypotension. Patients will be informed of this potential complication and instructed to contact the office and seek medical attention immediately for any syncopal or pre-syncopal events. Nitrate headaches are a common effect of ISDM and can often be controlled with aspirin or acetaminophen. Such adverse events are dose-related with a low incidence and occur more commonly in the elderly. They will also be told to have the patient lie down and elevate all four extremities to increase central pooling of blood. In the event of any severe reactions, the medication would be decreased to previously tolerated dose or stopped. Furthermore, this is a primary reason for the 3-5 day follow-up phone call. In Fontan patients, lowering blood pressure could also compromise kidney function which is why a 2 week follow-up visit will be performed to assess for any

significant changes to blood pressure at the discretion of the principal investigator based on patient baseline and normal blood pressure readings.

Patients under 18 having a positive pregnancy test will have the results reported to their parents and/or legal guardian. To mitigate the emotional risk from receiving a positive pregnancy result, study staff will offer chaplain services and/or a referral to counseling services. Lastly, there is a potential loss of confidentiality by participating in the study.

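### Background drugs may be changed between the two measurements of an uncontrolled pre/post comparison, and the analysis does not account for it

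*Combined protocol and SAP*

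**What the plan says.** **Handling of intolerance.** Three sections of the protocol bear on this.
- Proposed Dose, for patients who are symptomatic or not tolerating ISDN at a follow-up call: "attempts will be made to adjust background medications prior to lowering the ISDN dose". It makes no exception for severe reactions.
- Pharmacologic Interventions lists stepwise titration, acetaminophen for headache and a "recommendation to return to previous dose if necessary which may enhance tolerability". It does not mention background drugs and sets no order of actions.
- Potential Risks, Discomforts and Inconveniences: "In the event of any severe reactions, the medication would be decreased to previously tolerated dose or stopped".

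**Background drugs.** Entry requires patients to be "On a stable medication regimen for the past 3 months". No section requires the regimen to stay stable on study. The Visit 1 list includes "Demographic, medical, and medication review", and the "Medication review" row of Table 1 is marked at Visit 1 only. Visit 6 lists recovery of the vial and "Perform drug accountability", which concern the study drug. Pharmacologic Interventions does say that medication changes will be documented, in its text on patients who call the clinic. The Visit 2 to 5 phone calls are the planned contacts for adjusting medication.

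**Analysis.** The design is single-arm. Statistical Analyses compares every endpoint between the first and final visits and tests the mean VO2 change against zero at one-sided alpha 0.25. It treats a standardized change of at least 0.2 as encouraging, and sizes the later trial on the premise that placebo patients would not change. It has no rule for patients whose background drugs changed.

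**The concern.** With no control arm, the Visit 1 to Visit 6 change can be read as an ISDN effect only if nothing else relevant changed in between. The dosing rule permits such a change. A Visit 6 value then reflects ISDN plus the altered background regimen, and the analysis cannot separate the two.

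The patients affected are not a random subset, because the rule is triggered by poor tolerance of ISDN. The rule therefore also bears on the safety half of the primary objective and on the secondary objective about side effects under polypharmacy. Whether a patient stayed on ISDN unaided, or only after another drug was altered, is relevant to both.

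At stake are the estimated mean change and its SD. These are what the pilot is meant to hand to a confirmatory trial.

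**Working it through.** **1. The plan's own figures.** Inputs from Sample Size Calculation: n = 15, SD 7.
- Half-width of the 95% CI for the mean: t(0.975, 14) × 7/√15 = 3.88; the plan gives 3.9.
- 95% CI for the SD: 7 × √(14/χ²) gives 5.12 to 11.04, width 5.91; the plan gives 5.9.

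Both reproduce, and neither is in dispute.

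**2. Inputs the documents do not give.** They state no SD of within-patient change, no number of patients whose background drugs would be altered, and no size or direction of the resulting shift. All are assumed below. VO2 is in the plan's own units, which it does not name.
- SD of change = 7 × √(2(1 − r)), with equal SDs at both visits. For r = 0.7, 0.8 and 0.9 this is 5.42, 4.43 and 3.13.
- Patients affected: k = 5 or 3 of 15. Shift per affected patient: s = 2 or 3 units.
- True ISDN effect: zero.

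**3. Mean shift = k × s/15.**
- 5 × 2/15 = 0.67
- 5 × 3/15 = 1.00
- 3 × 2/15 = 0.40

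For k = 5 this is 0.67/5.42 = 0.12 SD up to 1.00/3.13 = 0.32 SD.

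**4. Chance of an observed standardized change of at least 0.2.** The threshold is t = 0.2 × √15 = 0.775 on 14 degrees of freedom. With no shift the probability is 22.6%. With a shift, the noncentral t (noncentrality = standardized shift × √15) gives:

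| Patients, shift | SD of change | Favourable | Unfavourable |
|---|---|---|---|
| 5 of 15, 2 units | 5.42 | 39% | 11% |
| 5 of 15, 2 units | 3.13 | 53% | 6% |
| 5 of 15, 3 units | 5.42 | 48% | 7% |
| 5 of 15, 3 units | 3.13 | 68% | 2% |
| 3 of 15, 2 units | 5.42 | 32% | 15% |
| 3 of 15, 2 units | 3.13 | 40% | 11% |

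The noncentral t moves everyone by the mean shift and so ignores the extra spread when only some patients move. Simulating a shift in the affected patients alone lowers the top figure from 68% to 65%; the others change less.

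**5. A reference point.** A shift of 1 SD of change in 3 of 15 patients moves the mean by 3 × 1/15 = 0.2 SD, the whole of the encouraging threshold. With the SDs above, that is 3.1 to 5.4 units per affected patient.

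**6. The passages side by side.** A patient with a severe reaction found at a follow-up call falls under both Proposed Dose (background drugs first) and the risk section (ISDN decreased or stopped). Neither defers to the other.

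**The case against.** **The strongest objection** is that this is a 15-patient pilot. Sample Size Calculation says null hypothesis testing is not directly related to the aims, and adjusting other drugs during titration is a legitimate design choice. The illustration also stacks assumptions. Both points stand, and they limit the severity. They do not remove the problem, because a shift in the mean change biases the estimate itself, and the estimate is the pilot's product.

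**Stronger readings the documents do not support:**
- *That the dosing rule contradicts two other sections.* Pharmacologic Interventions offers a return to the previous dose if needed and sets no order, so it is compatible. The risk section concerns severe reactions only. What remains is the missing exception in Proposed Dose.
- *That the stable-regimen criterion is breached, or exists so that patients serve as their own controls.* It is an entry criterion about the preceding three months, and no such purpose is stated.
- *That the changes would go unrecorded.* Pharmacologic Interventions provides for documenting medication changes, so those made by study staff should be on file. The gap concerns changes made outside study contacts, and the absence of any analysis that uses the record.
- *That poor tolerance is hidden.* The triggering symptoms meet the adverse event definition, are monitored at every visit and are reported as counts. Only the step taken to keep a patient on ISDN is left out of the planned safety report.
- *That the bias favours ISDN.* Nothing in the documents fixes its direction.

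**Conclusion.** The point holds as a should-fix. The plan permits background-drug changes between the two measurements and attributes the whole difference to ISDN. The resulting bias in VO2 and the haemodynamic endpoints has unknown size and direction. The range of 39-68% (favourable) or 2-11% (unfavourable), against about 23% with no shift, rests entirely on the assumed 5 of 15 patients, 2 to 3 units and correlation of 0.7 to 0.9. It shows that the 0.2 SD criterion is sensitive to such changes and is not a forecast. If no patient's background drugs are changed, there is no bias from this source.

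Separately, Proposed Dose and the risk section leave the order of actions for severe reactions unreconciled, and scheduled medication review ends at Visit 1.

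**What to change.** 1. **Statistical Analyses, efficacy.** Report the primary and haemodynamic changes for all patients, list those whose background drugs changed after Visit 1, and repeat the analysis without them as a sensitivity check only. The cost is precision and selection: the remaining patients are a subset chosen by tolerance of ISDN, so the result does not isolate the drug effect. If 5 of 15 were left out, the CI half-width would go from 2.145/√15 = 0.55 to 2.262/√10 = 0.72 SDs of change, about 29% wider at the same SD.
2. **Statistical Analyses, safety.** Report the number of patients whose background drugs were changed because of ISDN intolerance, alongside the adverse event counts. This is one added count.
3. **Table 1.** Mark medication review at Visit 6 and at the existing Visit 2 to 5 calls, and add it to the visit lists. No new contacts are needed.
4. **Protocol wording.** Reconcile Proposed Dose with Potential Risks, Discomforts and Inconveniences, and align Pharmacologic Interventions, so that one order of actions applies, including for severe reactions. Which order applies is for the investigators to decide.
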